### **B.6.22. Study Completion**

All subjects enrolled in the study are expected to complete all scheduled visits through the follow up visit 24 months after Device Activation for the test arm or 24 months after they are randomized to the control arm. If a control arm (CMM) subject crosses over to the test arm (DTM™ SCS), the subject will be followed for 12 months after device activation. If a test arm (DTM™ SCS) subject crosses over to the control arm (CMM), the subject will be followed until the 18 month follow-up visit. A Study Completion eCRF should be completed at the end of this visit. If there is an ongoing study related adverse event, subjects will be followed until resolution of that adverse event or determination that the adverse event is not expected to change (i.e. AE is stable).

### **B.6.23. Study Suspension and Termination**

Test subjects will be considered to have completed all study requirements following the completion of the follow up visit 24 Months after Device Activation and control subjects will be considered to have completed all study requirements following the completion of the 24 month follow up visit after randomization. Each clinical site will be considered to have completed study requirements at the end of the required monitored close out visit. The study will be considered terminated when all of the requirements of this Investigational Plan have been fulfilled, all close out visits have been completed and all Sponsor and Investigator reports have been issued and reported to the EC.

The Sponsor, the Investigators, or the EC(s) may suspend or terminate the study early at any time. If the study is suspended or terminated prematurely, all subjects that are still enrolled will be terminated from the study. A Study Completion eCRF will be completed noting that the study has been terminated. If there is an ongoing adverse event related to the device or treatment, the subject will be followed until resolution of the adverse event or determination that the adverse event is not likely to change.

In the event of suspension or termination of the study, subjects may be explanted according to Device Explant procedures. Subjects may choose to retain the implant and receive ongoing stimulation. Subsequent follow-up of the subjects after study completion will be the responsibility of the subject's personal physician.

The Sponsor reserves the right to terminate the study but intends only to exercise this right for reasons related to the protection of subjects or valid scientific or business reasons. The Sponsor will notify Investigators and ECs in writing in the event of study termination.

The Sponsor reserves the right to stop the enrollment of subjects at any clinical site at any time after the clinical site initiation. Possible reasons for suspending or terminating a clinical site may include, but are not limited to:

- Non-compliance by Investigator
- Failure to obtain proper written informed consent
- Repeated failure to complete or submit eCRFs in a timely manner
- Failure to report SAEs to the Sponsor within 24 hours of knowledge of the event and to reviewing EC in accordance with its policies
- Repeated failure to comply with clearance of queries generated during monitoring of the study

- Inactivity

## B.7. Study Endpoints

### B.7.1. Definition of Analysis Populations

- Modified Intent to Treat (mITT): All randomized subjects to the test arms who successfully complete the Trial Phase and all successfully randomized subjects to the control arm.
- Intent-to-Treat (ITT): All successfully randomized subjects who met all the enrollment criteria.
- Per-Protocol (PP): All test subjects who received a permanent device implant and all control subjects who contributed their data to the primary and secondary endpoint without any major protocol deviations (that would render their data unevaluable).

The primary analysis of the primary and secondary endpoints will be performed on the mITT population. Supportive analyses will be performed for the Intent-to-Treat and Per-Protocol population.

For secondary endpoint analyses incorporating crossover data (i.e. data gathered in the post 6-month periods), sensitivity analyses will be performed to examine the impact of crossover.

### B.7.2. Effectiveness Assessment Definitions

- Primary Effectiveness Assessment: For test subjects who have a successful Trial Phase and receive a permanent implant, the Primary Efficacy Assessment occurs at the follow up visit 6 months after Device Activation. For subjects who do not have a successful Trial Phase (based on subject's pain score) or subjects who do not want a permanent device implant due to insufficient pain relief (based on subject's discontinuation reason), the Primary Efficacy Assessment occurs at the end of the Trial Phase. For control arm subjects, the Primary Efficacy Assessment occurs at the 6 months follow up visit post-randomization.

### B.7.3. Primary Endpoint

Pain rating on the 10 cm Visual Analog Scale (VAS) is considered the primary outcome measure. VAS is the most widely used outcome measure in assessing pain due to its documented reliability and validity, ease in administration, and minimal training requirements for the administrator.

- ***Individual Responder:*** A decrease in back pain VAS by at least 50% at 6 months Post-Permanent Device Activation (Test group) or 6 months post-randomization (Control group) as compared with Baseline.

**Overall Study Success:** The percentage of Individual Responders in the test group is shown to be statistically superior to the percentage of Individual Responders in the control group.

#### B.7.4. Secondary Endpoints

The following secondary endpoints will be evaluated:

- Comparison of the percentage of Individual Responders between the test and control groups in a statistical test of superiority over time. In addition, data will be summarized at the individual time points at 1 month, 3 months, 6 months, 9 months, 12 months, 18 months, and 24 months.
- Comparison of change from Baseline in VAS back pain score between test and control in statistical tests of non-inferiority and superiority at 1 month, 3 months, 6 months, 9 months, 12 months, 18 months, and 24 months . This is calculated as: Change from Baseline in Back Pain VAS = Follow-up Visit Pain VAS – Baseline Pain VAS. A negative result reflects a decrease in the Pain VAS, while a positive result reflects an increase in Pain VAS.

Analysis of results through 6 months will be based on the mITT population. Sensitivity analysis of both secondary endpoints will also be performed to assess the impact of crossover.

### B.7.6. Safety

Safety will be assessed by characterizing clinically meaningful change in adverse events at all study visits.

#### Definitions

An **Adverse Event** (AE) is any untoward medical occurrence defined as an unintended disease or injury or untoward clinical signs (including abnormal laboratory findings deemed clinically significant as determined by the investigator) in a subject whether or not related to the investigational or commercial medical device. This definition includes events related to the study medical devices and events related to the study procedures. An AE is also any event related to any underlying medical condition, present at Baseline, which increases in severity by a clinically meaningful amount during the study as determined by the Investigator.

For all adverse events, the Investigator will provide an assessment of the adverse event, its severity, treatment/intervention provided, relationship to the device/procedure, and resolution.

As the primary efficacy measure in this study is pain, back or leg pain does *not* need to be reported as an adverse event unless it meets the definition of a serious adverse event. However, Investigators may, at their discretion, report any pain-related adverse events during the study.

Pre-existing conditions will not be reported as an adverse event unless there has been a substantial increase in the severity or frequency of the problem which has not been

attributed to natural history.

**A Serious Adverse Event (SAE)** is an adverse event that

- Led to death
- Led to serious deterioration in the health of the subject, that either resulted in
  - a life-threatening illness or injury (life-threatening is defined as at risk of death at the time of the event), or
  - a permanent impairment of a body structure or a body function, or
  - in-patient hospitalization or prolongation of existing hospitalization (in-patient hospitalization is defined as a hospital admission for a period of greater than 24 hours), or
  - medical or surgical intervention to prevent life-threatening illness or injury or permanent impairment to a body structure or a body function,
- Led to fetal distress, fetal death, or a congenital abnormality or birth defect

Those known adverse events related to the device, procedure or therapy are listed in the Risk Analysis Section C.

**A Serious Adverse Device Effect (SADE)** is an adverse device effect that has resulted in any of the consequences characteristic of a serious adverse event.

An **Unanticipated Serious Adverse Device Effect (USADE)** is a serious adverse device effect which by its nature, incidence, severity or outcome has not been identified in the current version of the risk analysis report. Additionally, an **Anticipated Serious Adverse Device Effect (ASADE)** is an effect which by its nature, incidence, severity or outcome has been identified in the risk analysis report.

Those known adverse events related to the device, procedure or therapy are listed in the Risk Analysis Section C.

An anticipated serious adverse device effect (ASADE) is a serious adverse device effect which by its nature, incidence, severity or outcome has been previously identified in the risk analysis report. Untoward medical occurrences that are not unanticipated, i.e. are unsurprising, are identified in the Physician Manual or Protocol and ICF.

Those known adverse events related to the device, procedure or therapy are listed in Section C.

Device deficiencies will be handled under the post-market surveillance/vigilance system from the manufacturer (i.e. Medtronic) as the Intellis system is a CE marked device which meets vigilance reporting criteria.

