## **B.2. Study Objectives**

The **primary objective** of this study is to evaluate the clinical effectiveness of DTM™ SCS with CMM in reducing back pain as compared to CMM alone for the treatment of intractable chronic back pain.

The **secondary objectives** of this study are to further document the safety, clinical effectiveness and health economic analytics of the DTM™ SCS delivered through Intellis™ system when compared to CMM alone, for the treatment of chronic pain of the trunk and limbs.

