### Control treatment group: Conventional Medical Management (CMM)

- The choice of appropriate Conventional Medical Management will be **made by the Investigator as determined to be the best standard of care** for each individual subject i.e. optimized individual conventional therapy. These treatments would be generally consistent with the American College of Physicians and the American Pain Society Guidelines as published in the Annals of Internal Medicine (<http://annals.org/article.aspx?articleid=736814>) and European/UK guidelines. The CMM treatment can be modified at any moment by the investigators based on their clinical evaluation and local standard of care. They may also consist of one or more of the following treatments:
  - Medications: Over-the-counter analgesic medications, opioid medications, nonsteroidal anti-inflammatory drugs (NSAIDs), anticonvulsants, antidepressants, topical analgesics
  - Combined physical and psychological management (CPPM)
  - Physical therapy
  - Back rehabilitation program
  - Spinal manipulation and spinal mobilization
  - Traction
  - Acupuncture
  - Cognitive behavioral therapy (CBT)
  - Biofeedback
  - Nerve blocks
  - Radio frequency ablation
  - Epidural steroid injections
  - Transcutaneous electrical nerve stimulation (TENS)
  - Intradiscal electrothermal therapy (IDET)
  - Nucleoplasty, also called plasma disc decompression (PDD) or similar

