## **Reporting**

All device or procedure-related adverse events will be captured from enrollment through the completion of the study on the Adverse Event Case Report Form (CRF). However, in accordance with ISO 14155 latest version when using commercial medical devices, device deficiencies, SAEs, SADEs and USADEs must be reported per the post-market surveillance/vigilance system of the manufacturer as specified in the manufacturer's labeling/manuals.

All AEs, Device Deficiencies, SAEs, SADEs and USADEs (see list in section C) reported during the study will document severity, treatment/intervention provided, relationship to the device/procedure, and resolution. Any USADEs and/or deaths occurring during the study procedures will also be evaluated to determine whether the SCS system might have malfunctioned, or caused or contributed to the event.

All SAEs/SADEs/USADEs will be documented and reported to SGX as soon as possible, but no later than 24 hours after becoming aware of the SAE.

The SGX contact information for these events is or reporting through eCRF:

E-mail: [[contact]](mailto:[contact])

The Investigator or site staff may report an event to the sponsor by email, telephone or fax initially, but must follow-up by completing an Adverse Event CRF. The monitored CRF should be sent to SGX and, if possible, be accompanied by copies of source documentation regarding the event (e.g., physician / nurse notes or summaries / hospitalizations records). The Investigator must also report the SAE to the EC according to their local regulations.

An attempt must be made by the Investigator/site staff to schedule a subject visit as soon as feasible following the report of the SAE. In the event of a subject death, all available information (e.g. autopsy or other post-mortem findings) should be provided on the CRF. An Investigator shall submit a report to the sponsor of any USADE occurring during the study as soon as possible, but in no event later than 10 working days after the Investigator first learns of the effect. SGX will conduct an evaluation of the event to determine whether the event is an anticipated event based on labeling and risk analysis. The Investigator must also report the event to the EC if it is determined to be unanticipated.

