All AEs will be followed until the event is resolved (with or without sequelae). If a device-related event is ongoing at the time of study completion or termination, the subject will be followed until resolution or the Investigator determines that the subject's condition is stable.

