5.9 Safety Analyses

Safety will be assessed by characterizing adverse events at all study visits with descriptive statistics.

All Adverse Events assessed/determined to be study-related study will document seriousness, severity, treatment/intervention provided, relationship to the device/procedure, and resolution.

Adverse events (AE) will be reported for the mITT set. A sensitivity analysis of AEs based on the ITT set will also be performed. AEs will be tabulated with the number of events and subjects with event for each event type and overall. Rates will be reported as the number of subjects who experience at least one event during the analysis interval out of the total number of subjects with follow-up to the beginning of the analysis interval. Serious adverse events will also be tabulated. The rate of all AEs and SAEs reported in the study will be reported.

All AEs and SAEs will also be summarized by relatedness as described above. Adverse events leading to death or study discontinuation will be provided in listing format.

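### The plan names no category for adverse events related to conventional medical management (CMM), so its related-event summary cannot show CMM-caused harm on the same footing as device harm

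*Protocol*

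**What the plan says.** **Objective.** Protocol B.2 includes among the secondary objectives to "further document the safety, clinical effectiveness and health economic analytics of the DTM™ SCS delivered through Intellis™ system when compared to CMM alone".

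**What counts as an AE.** The B.7.6 definition is all-cause: an event counts "in a subject whether or not related to the investigational or commercial medical device".

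**What is attributed.** B.7.6 Definitions says that, for every AE, "the Investigator will provide an assessment of the adverse event, its severity, treatment/intervention provided, relationship to the device/procedure, and resolution". B.7.6 Reporting says much the same of events that are "reported during the study will document severity, treatment/intervention provided, relationship to the device/procedure, and resolution". SAP 5.9 uses the same object, and adds: "All AEs and SAEs will also be summarized by relatedness as described above".

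**What CMM contains.** B.4 lists "Medications: Over-the-counter analgesic medications, opioid medications, nonsteroidal anti-inflammatory drugs (NSAIDs), anticonvulsants, antidepressants, topical analgesics". It also lists nerve blocks, radio frequency ablation, epidural steroid injections, IDET and nucleoplasty. The test group receives CMM as well as SCS.

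**Wider wording elsewhere.** B.8.2 (Safety Measurements) asks investigators to categorize relationship without saying to what, and then mentions only device relation. E.3 speaks of relationship to the study. SAP 5.9 opens its attribution sentence with study-related events. None of these terms is defined.

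**Follow-up of ongoing events.** B.7.6 Reporting first says that all AEs are followed to resolution, and then: "If a device-related event is ongoing at the time of study completion or termination, the subject will be followed until resolution" (or until the condition is judged stable). B.6.15, B.6.16 and B.6.22 use *study related* for the same purpose. B.6.23 refers to the device or treatment.

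**The concern.** Both arms receive treatments that can cause harm, but the plan names an attribution category for only one of them. An opioid or NSAID reaction is caused by neither a device nor a procedure. An investigator who follows B.7.6 as written must score it unrelated, in the control arm and in the test arm alike. Capturing every event would not change this, because the gap lies in how a captured event is classified.

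At stake is the descriptive safety comparison named in B.2. If the relatedness summary were read across arms, SCS harms would be compared with a control column that has no place for drug harms. The same summary would also leave CMM drug harm in the test arm uncounted. All-cause rates would include these events, but a reader could not separate those that investigators judged to be caused by CMM from intercurrent illness.

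**Working it through.** The plan gives no figure on this point, so there is none to reproduce. The check is mainly textual.

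**Step 1. Is there a category for CMM?** Objects of attribution, side by side:

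| Place | Object of relatedness | Names CMM? |
|---|---|---|
| Protocol B.7.6 Definitions | device/procedure | No |
| Protocol B.7.6 Reporting | device/procedure | No |
| Protocol B.8.2 Safety Measurements | none stated, then device | No |
| Protocol E.3 | the study | No |
| SAP 5.9 | study-related events, then device/procedure | No |

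The documents are inconsistent rather than uniformly device-only, but no row supplies a CMM category. The SAP's back-reference for the relatedness summary points to its own device/procedure wording.

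**Step 2. What does *procedure* cover?** It is not defined. Protocol A.2 uses it for the SCS trial and permanent implant, and the exceptional-circumstances text in B.9.1 uses *procedural* for trial and IPG visits. B.7.6 also mentions study procedures, and known events related to therapy, but it refers the latter to Section C, which describes no CMM risk. The SCS reading is the likelier one. A site could still read the word to include a nerve block or an epidural injection.

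**Step 3. Consequence by type of harm.**
- CMM drug reaction: unrelated under either reading, in either arm.
- CMM intervention harm: unrelated under the SCS reading, related under the broad reading.
- SCS device or implant harm: related under either reading.

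**Step 4. Illustration of size.** Inputs: 150 subjects randomized 1:1 (B.5.5.2 and B.4), so 150 / 2 = 75 controls. The documents give no rate of CMM-caused events, so two quantities are assumed: *r*, the share of controls with a CMM-caused AE, and *q*, the share of those subjects whose event is coded as procedure-related.

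Subjects with a CMM-caused AE = 75 × *r*. Subjects recorded as related = 75 × *r* × *q*.

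| *r* | 75 × *r* | *q* = 0 | *q* = 25% | *q* = 50% | *q* = 100% |
|---|---|---|---|---|---|
| 5% | 3.75 | 0 | 0.94 | 1.88 | 3.75 |
| 10% | 7.5 | 0 | 1.88 | 3.75 | 7.5 |
| 20% | 15 | 0 | 3.75 | 7.5 | 15 |
| 30% | 22.5 | 0 | 5.63 | 11.25 | 22.5 |

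The SCS reading gives *q* = 0. Under the broad reading *q* can reach 100% only if every affected subject has an intervention-related event, since drug reactions cannot be coded as procedure-related. The all-cause count does not depend on *q*.

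**Step 5. What else does SAP 5.9 report?** It tabulates AEs by event type and overall, tabulates serious AEs, and reports rates of all AEs and SAEs. CMM harms that reach the AE form appear there. It does not say that any of these tables, or the relatedness summary, is split by arm.

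**The case against.** The strongest reply has five parts.

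1. **All-cause rates are planned.** In an open-label randomized trial they are less exposed to subjective attribution than any relatedness split. This stands, and it confines the point to the relatedness summary. One condition applies: B.7.6 Reporting names only device- or procedure-related events for capture on the AE form, which sits badly with the all-cause definition.
2. **Wider relatedness terms exist** in B.8.2, E.3 and SAP 5.9, and a control subject could meet them. This stands as evidence of inconsistency. It does not supply a CMM category or say how such events enter the summary.
3. **The AE form is not among the documents.** The SAP is to be read with the case report forms, and the form may already carry a treatment-relationship field. This stands, so the form change is conditional.
4. **No safety hypothesis or success criterion depends on it.** Safety is descriptive, and study success rests on the primary endpoint. This stands and limits the weight of the point.
5. **The follow-up wording is not arm-specific.** B.6.15 uses *study related* for the test arm too, and B.7.6 Reporting begins with all AEs. This stands, and what remains is a wording inconsistency.

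A reader might go further and infer that related harm in the control arm is near zero by construction and that the comparison is therefore biased against the device. The documents do not support that as a general statement. It requires the SCS reading of an undefined word and a by-arm relatedness table that SAP 5.9 does not specify. It also fails after month 6 if events are counted as randomized, because controls who cross over can have device-related events. Before crossover, a zero device-related rate in subjects without a device is simply correct.

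**Conclusion.** The point holds in a limited form. The plan names no relatedness category for CMM, and SAP 5.9 summarizes AEs and SAEs by a relatedness whose stated object is the device or procedure. For CMM drugs the gap does not depend on interpretation. For CMM interventions it depends on *procedure* meaning the SCS trial and implant, which is likely but not stated. Followed as written, the related-event summary cannot set CMM-caused harm beside device harm, although safety against CMM alone is a stated secondary objective.

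The number of subjects affected cannot be derived from the documents. The figures of about 4 to 23 of 75 controls rest on an assumed 5% to 30% with a CMM-caused event and show scale only. The primary endpoint and the all-cause safety rates do not depend on this gap. The change should be made because a stated objective is affected and the remedy is cheap.

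**What to change.** 1. In Protocol B.7.6, define *procedure*.
2. For every AE in both arms, record relatedness separately to (a) the SCS device or stimulation, (b) the SCS trial or implant procedure, (c) CMM medication and (d) a CMM intervention. Add these choices to the AE form if it does not already have them.
3. Align B.7.6 Definitions, B.7.6 Reporting, B.8.2 Safety Measurements, E.3 and SAP 5.9 on that single scheme.
4. In SAP 5.9, tabulate by arm all-cause AEs and SAEs, as the main between-arm safety comparison, and also AEs related to any assigned treatment with the four-way split. State how events after crossover are counted.
5. Reconcile the differing wording on follow-up of ongoing events in B.6.15, B.6.16, B.6.22, B.6.23 and B.7.6 Reporting.

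The cost is a few choices on the form, some wording in both documents and one further table split. The downside is slightly more work per event, and re-attribution of events already entered.

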### **B.5.4. Blinding**

Due to the nature of the treatment groups, comparing an implantable medical device with conventional medical management that may involve multiple different treatments, it is not feasible to blind the subjects, implanting physicians or the clinical site personnel to the group assignments. The assessment of treatments are done by the subjects and not by the site personnel, so the lack of blinding of site personnel should not affect results as pain is the major assessment and subjects tend to describe pain truthfully since it affects their everyday life dramatically and not be influenced by knowledge of which treatment arm

they are assigned to. In order to minimize potential assessment bias, the subjects will receive the standard instructions for completing the questionnaires.

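### Protocol B.7.6 gives two conflicting rules for worsening of a pre-existing condition; the narrower one makes an unblinded causal opinion a filter on recording and leaves serious events unclear

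*Protocol*

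**What the plan says.** Protocol B.7.6, Definitions, opens with a broad AE definition. It covers untoward occurrences "in a subject whether or not related to the investigational or commercial medical device", and it adds: "An AE is also any event related to any underlying medical condition, present at Baseline, which increases in severity by a clinically meaningful amount". The investigator decides whether that amount has been reached.

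Two exemptions follow. Back or leg pain need not be "reported as an adverse event unless it meets the definition of a serious adverse event". The second exemption concerns conditions that a subject already had on entry: "Pre-existing conditions will not be reported as an adverse event unless there has been a substantial increase in the severity or frequency of the problem". That sentence runs over a page break and ends by requiring that the increase has not been "attributed to natural history".

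The serious adverse event (SAE) definition comes next and is built on the AE: an SAE is an AE with one of the listed consequences. Under Reporting, SAEs must reach the sponsor within 24 hours of awareness. The same part says that AEs related to the device or procedure are captured on the AE form. B.8.2 (Safety Measurements) is wider, asking for a form whenever an AE occurs, and it leaves severity, device relation and resolution to the investigator. B.5.4 states that "it is not feasible to blind the subjects, implanting physicians or the clinical site personnel". SAP 5.9 tabulates AEs and SAEs with descriptive statistics.

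**The concern.** The same event can be an AE under one sentence and unreported under another a few lines later. Sites have no instruction on which to follow, so practice may vary between sites and between investigators.

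The narrower sentence also uses causality at the wrong step. Whether a worsening reflects the natural course of a disease belongs in the relationship assessment, where the event stays in the data and can be reviewed. Here the same opinion decides whether a record exists. The people likely to hold it know the treatment arm, and no independent adjudication is described.

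Documenting safety compared with conventional medical management (CMM) alone is a stated objective (Protocol B.2). If worsening is put down to natural history more readily in one arm, the reported rates will differ for a reason unrelated to harm. The absence of a serious-event exception is the most consequential part, because SAEs are the events a safety description can least afford to lose.

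**Working it through.** The plan states no figure on this point, so the check is a comparison of texts followed by an illustration.

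**Step 1. The rules side by side (Protocol B.7.6, Definitions)**

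| Feature | AE definition | Pre-existing-condition sentence | Back/leg pain sentence |
|---|---|---|---|
| Threshold | clinically meaningful | substantial | serious events only |
| What must increase | severity | severity or frequency | not applicable |
| Excluded if thought to be natural history | no | yes | no |
| Exception for serious events | not needed | none | yes |

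**Step 2. Apply both rules to the same case**

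- *Clinically meaningful but not substantial worsening:* an AE under the definition; not reported under the later sentence.
- *Substantial worsening, attributed to natural history:* an AE under the definition; not reported under the later sentence.
- *The same, with an admission of more than 24 hours:* under the definition it is an AE, meets the SAE criteria and falls under the 24-hour rule. Under the later sentence it is not reported as an AE. Since an SAE is defined as a kind of AE, a site may never reach the serious criteria.
- *Substantial worsening in severity, not attributed to natural history:* reported under both.

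The rules agree only in the last case. The later sentence cannot be a mere working version of the definition, because it removes events that the definition includes.

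**Step 3. Who makes the attribution**

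The sentence is passive and names nobody. The AE definition leaves clinical meaningfulness to the investigator, and B.8.2 leaves severity and device relation to the investigator. The natural reading is therefore the investigator, who is unblinded under B.5.4. This is an inference.

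**Step 4. Does another section resolve it?**

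The 24-hour rule applies to events already classed as SAEs, so it does not settle the third case. The capture sentence under Reporting names only device- or procedure-related AEs, which conflicts with the definition's indifference to relatedness and with B.8.2. SAP 5.9 refers in one place to study-related events and in another to the rate of all AEs and SAEs. None of these reconciles the two sentences.

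**Step 5. Illustration (assumed inputs)**

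Reported rate = true rate of worsening × (1 − share attributed to natural history). The true rate is assumed equal in both arms.

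| True rate | 20% attributed in both arms | 20% in one arm, 50% in the other |
|---|---|---|
| 5% | 4.0% v. 4.0% | 4.0% v. 2.5% |
| 10% | 8.0% v. 8.0% | 8.0% v. 5.0% |
| 20% | 16.0% v. 16.0% | 16.0% v. 10.0% |

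With equal attribution the arms stay equal, although both are under-reported. With unequal attribution a difference appears from the filter alone. The ratio, 0.8/0.5 = 1.6, depends only on the assumed shares, and swapping the arms reverses it.

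**The case against.** The best defence is that the broader rule already protects serious events. A clinically meaningful worsening is an AE by definition; if it leads to a qualifying hospital admission it is an SAE, and all SAEs must be reported within 24 hours. This has force. A reader might infer that a serious worsening called natural history is never recorded. The documents do not say that. They support only that the duty is unclear and that a site applying the narrower sentence could omit the event.

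A reader might also infer that SAP 5.9 compares AE and SAE rates between arms. It states no between-arm safety test or hypothesis, and the protocol's Definition of Success sets no success criterion beyond the primary endpoint. What stands is that even a descriptive account is incomplete if events are filtered out before recording.

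Third, much worsening in this population will be back or leg pain, which has its own sentence with an explicit exception for serious events, and back pain scores are collected at scheduled visits. The gap for serious events therefore concerns mainly other conditions. That narrows the point without removing it.

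Fourth, the definition itself rests on the unblinded investigator's judgement, so changing the threshold word does not remove discretion. That is correct. The main gain comes from deleting the causal exclusion, so that the judgement about cause is recorded alongside the event.

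Finally, it could be said that unrelated worsening is outside the capture sentence anyway. That sentence conflicts with the definition and with B.8.2, so it is a second inconsistency and not a defence.

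**Conclusion.** The conflict is real and visible on the face of B.7.6. Two sentences treat the same worsening differently, the narrower one makes a causal opinion a condition of recording, and the duty to report serious worsening attributed to natural history, mainly of conditions other than back or leg pain, is left unclear. It should be corrected.

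The size cannot be stated. The documents give neither AE rates nor attribution rates, and the direction could favour either arm. A reader might take an illustration as evidence of a large artefact: for example, 60% v. 20% attribution at a true 10% gives 10% × 0.4 = 4% v. 10% × 0.8 = 8%, a twofold difference. That ratio is simply the assumption restated, and the documents offer no support for it.

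The conclusion assumes that at least some sites would follow the narrower sentence and that the investigator makes the attribution. Distortion between arms further requires attribution to differ by arm, which is possible in an open-label trial but not shown.

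**What to change.** In Protocol B.7.6, Definitions, replace the pre-existing-condition sentence with one rule that matches the AE definition: a clinically meaningful increase in the severity or frequency of a pre-existing condition is reported as an AE, whatever its presumed cause. Add frequency to the definition so that the two agree. State that presumed natural history is entered in the causality assessment and is not a reason to withhold a report. State that any event meeting the SAE criteria is always reported.

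In B.7.6, Reporting, align the sentence limiting AE form capture to device- or procedure-related events with the definition, B.8.2 and SAP 5.9, so that AEs are captured whether or not related. Without this second edit, a worsening judged unrelated could still be left off the form.

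The cost is the amended wording, brief site training, more AE forms and slightly higher AE counts. Treatment, endpoints and sample size are unaffected.
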